13.6 Multicenter Study - Pooling

All study data will be pooled across study sites to facilitate hypothesis testing in accordance with the sample size estimation and power analysis (Section 13.3). Pooling is generally justified because the study will be conducted such that: 1) the same protocol will be used at each site; 2) site investigators and personnel will receive uniform training; and 3) central data management and monitoring will be consistent and applied with equal rigor at all sites. Primary endpoint results, demographics and baseline characteristics will be summarized by site and evaluated for comparability among study sites.

13.7 Subject Disposition

A detailed description of subject disposition will be provided using a CONSORT diagram and summaries of subjects falling in various subgroups of interest, such as, enrolled but not treated, discontinued, deaths, and withdrawals. Follow-up by visit will be presented, showing theoretical, expected, and actual follow-up visits.

13.8 Demographics and Baseline Characteristics

Demographics and baseline characteristics will be summarized using frequencies and percentages for categorical factors and mean, median, standard deviation, minimum and maximum for continuous factors.

13.9 Primary Efficacy Endpoint Analysis

The mean change in the rTNSS score from baseline to 12 weeks will be tested using a paired t-test for a significant decrease greater than the MCID under the one-sided null (H_0) and alternative (H_A) hypotheses:

H₀:
$$\mu_d \ge -1$$

 $H_A: \mu_d < -1$

where μ_d = the mean change of the paired differences of the 12-week score - the baseline score.

A p-value for the test statistic ≤ 0.05 will indicate that the mean decrease is statistically significantly greater than 1 point. The upper limit of the one-sided 95% confidence interval on the mean decrease will also be calculated.

13.10 Other Efficacy Outcome Measures

13.10.1 Responder Rate

Subjects will be considered to have responded to treatment if they show a decrease of at least 1 point in the rTNSS score at 12 weeks compared to baseline score. An overall responder rate of at least 55% is expected for the study.

13.10.2 rTNSS scores over time

Summary descriptive statistics (mean, SD, median, range) for the rTNSS scores and change from baseline will be summarized at baseline and for each follow-up evaluation.

13.10.3 rTNSS individual nasal symptom scores

The distribution of responses (frequency, percentage) and the mean (SD, median, range) response, based on the 4-point response scale, for each of the survey questions will be summarized at baseline and for each follow-up evaluation.

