1.0 PROTOCOL SYNOPSIS

Study Title:	Clinical Evaluation of Low Power Radiofrequency Energy Applied to the Posterior Nasal Nerve Area for Symptomatic Relief of Chronic Rhinitis
Study Device:	Aerin Medical InSeca ARC Stylus
Device Description:	The InSeca ARC Stylus is a disposable handheld device capable of delivering bipolar radiofrequency energy to tissue.
Indication:	The InSeca ARC Stylus is indicated for use in otorhinolaryngology (ENT) surgery for the coagulation of soft tissue in the nasal airway, to treat nasal airway obstruction by shrinking submucosal tissue.
Study Objective:	The primary objective of this study is to collect clinical data on the use of the InSeca ARC System to treat tissue in the posterior nasal nerve area to improve symptoms in adults diagnosed with chronic rhinitis.
Study Design:	Prospective, multicenter, nonrandomized, nonsignificant Risk (NSR) study.
Subject Population:	Male and female subjects who present with symptoms associated with chronic rhinitis and meet the protocol eligibility criteria.
Study Procedure:	Subjects will have BOTH nostrils treated in the portion of the nasal cavity mucosa overlying the region of the posterior nasal nerve (the posterior middle meatus and posterior inferior meatus). Follow-up visits will be scheduled and calculated from the treatment date. No repeat ("touch-up") procedures will be permitted during the 52-week follow-up period.
Study Endpoints:	Primary Efficacy Endpoint : Mean change in the rTNSS score from baseline to 12 weeks post study procedure. For study success, the mean change must show an improvement (decrease) exceeding 1 point.
	Primary Safety Endpoint : Safety will be assessed by characterizing the type and frequency of adverse events reported at or following the study procedure, and throughout the follow-up period.
Additional Evaluations:	Responder Rate : A responder is defined as a treated subject who experiences at least a 1 point improvement (decrease) in the rTNSS score at 12 weeks compared to baseline score. An overall responder rate of at least 55% is expected for the study.
	rTNSS Scores Over Time : rTNSS scores and change from baseline will be summarized at baseline and each follow-up evaluation.
	rTNSS Individual Nasal Symptom Scores : The scores of each survey question will be summarized at baseline and each follow-up evaluation.

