8.5 Types of Assessments

The following assessments will be obtained from the study subjects at the specified study follow-up visits:

Total Nasal Symptom Score (TNSS) – The TNSS is an instrument used to collect patient selfrated severity of four nasal symptoms: rhinorrhea, nasal congestion, nasal itching and sneezing. The FDA cites this as a preferred measure of efficacy in trials of drug treatments for allergic rhinitis¹⁷ and nonallergic rhinitis¹⁸. The TNSS requires the subject to rate four nasal symptoms (rhinorrhea, nasal congestion, nasal itching and sneezing) on the following 4-point scale:

- 0 = absent symptoms (no sign/symptom is evident)
- 1 = mild symptom (sign/symptom present, but minimal awareness; easily tolerated)
- 2 = moderate symptoms (definite awareness of sign/symptom that is bothersome but tolerable)
- 3 = severe symptoms (sign/symptoms that is hard to tolerate; causes interference with activities of daily living and/or sleeping)

For the purposes of this study, the subject will be asked to evaluate symptom severity over the preceding 12 hours.

Do not copy, distribute, or share with others without prior written authorization from Aerin Medical Inc.

Visual Assessment of Treatment Area – The target posterior nasal nerve area within each nostril will be visually assessed at baseline and following the treatment procedure at the time points described in Table 1. The use of an endoscope for visual assessment is required. For consistency in reporting across sites, a study CRF will outline specific observations to be assessed.

Video should be captured and archived during the endoscopic evaluation. These videos will allow for future evaluation or comparison, if necessary. If video capture is unavailable, representative still photographs may be collected instead.

Visual Analog Scale (VAS) for Pain Intensity¹⁹ – The Pain VAS will be used to rate pain associated with the treatment (i.e., in the treatment area) immediately following the procedure and at each follow-up visit through 12 weeks. Subjects will be asked to mark their pain level on a 10-cm line anchored by verbal descriptors: 0 = no pain and 10 = worst pain imaginable. The study staff will measure with a metric ruler from the 0, the beginning of the line, to the vertical mark made by the subject. The result, expressed in millimeters, will represent the subject's VAS Pain Score.

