13.3 Sample Size Estimate

Sample size estimation was based on a paired t-test for change from baseline at 12 weeks using the following assumptions:

- Significance level $\alpha = 0.05$ (one-sided)
- Power = 90%
- MCID = 1-point decrease in mean change score = the minimum clinically important difference
- μ_d = -2-point decrease in mean change score = the minimum expected observed difference
- SD = 2 = the expected standard deviation of the observed mean difference
- 10% dropout and nonevaluable.

The minimum number of subjects to achieve 90% power is 36 (G-Power, paired t-test).

The overall planned study sample size is 50 subjects. Fifty subjects allows for the possibility that findings from the review of the phase-1 initial subjects, with respect to the planned protocol treatment parameters, leads to significant protocol modifications to the procedure parameters for the remainder of the subjects. Significant modifications would exclude the initial subjects from the primary endpoint analysis, but a sufficient number of subjects would remain for analysis of the primary study hypothesis.

The sample size estimate will be re-evaluated after the standard deviation of the mean change for the phase-1 initial subjects has been obtained. If the observed standard deviation is larger than the assumed standard deviation, the sample size may be recalculated to assure adequate study size to evaluate the study hypothesis. This evaluation will not be an efficacy evaluation and will not be used to halt the study based on an early determination of success or to decrease the planned sample size.

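### Is the expected responder rate of at least 55% too lax to be left in the plan without a derivation?

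*Combined protocol and SAP*

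**What the plan says.** The synopsis (section 1.0, Additional Evaluations) defines a responder as a treated subject with "at least a 1 point improvement (decrease) in the rTNSS score at 12 weeks compared to baseline score". Section 13.10.1 repeats this as "a decrease of at least 1 point in the rTNSS score at 12 weeks compared to baseline score" and adds "An overall responder rate of at least 55% is expected for the study". Both places list the measure among additional or other efficacy outcomes, and neither attaches a hypothesis, a test or a decision to it.

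The success rule stands elsewhere. Under Study Endpoints the synopsis says "For study success, the mean change must show an improvement (decrease) exceeding 1 point". Section 13.9 tests this with a one-sided paired t-test and reads a p-value of 0.05 or less as showing that "the mean decrease is statistically significantly greater than 1 point".

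The planning values are in section 13.3: "2-point decrease in mean change score = the minimum expected observed difference" and "SD = 2 = the expected standard deviation of the observed mean difference". Section 8.5 describes the instrument: "The TNSS requires the subject to rate four nasal symptoms (rhinorrhea, nasal congestion, nasal itching and sneezing) on the following 4-point scale". The points run from 0 to 3, and section 7.2 gives a maximum total of 12.

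**The concern.** The 55% is the only numerical target among the additional evaluations. The plan neither derives it nor gives a source, and it is not linked to the mean and SD used for the sample size. The responder cut is also the same 1 point that forms the null value of the primary test, applied to the same 12-week change. A rate just above one half could therefore come from a study whose mean decrease is no greater than 1.

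The study has a single arm, so no control rate exists against which to judge the figure. A report could state that the expected responder rate was reached although the primary test failed, and a reader might take this as separate support.

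**Working it through.** **Inputs.** Section 13.3: null value 1, planned mean decrease 2, SD 2, one-sided alpha 0.05, power 90%, minimum 36 subjects, planned 50. Section 8.5: four items scored 0 to 3, so individual changes are whole points. *Assumption not in the documents:* changes follow a normal distribution rounded to whole points, with no floor or ceiling effect.

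**The plan's own figure.** A one-sided paired t-test with shift 2 − 1 = 1 and SD 2, using the noncentral t distribution, has power 89.5% at n = 35 and 90.3% at n = 36. The stated minimum of 36 is reproduced. It follows when the SD of 2 is read as the SD of individual changes, and that reading is used below.

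**Expected responder rate.** With mean decrease m, a recorded decrease of at least 1 corresponds to at least 0.5 before rounding, so the rate is Φ((m − 0.5)/2). Treating the score as continuous gives Φ((m − 1)/2), shown only as a sensitivity reading.

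| True mean decrease | Whole-number score | Continuous reading |
|---|---|---|
| 0 | Φ(−0.25) = 40.1% | Φ(−0.5) = 30.9% |
| 1 (null boundary) | Φ(0.25) = 59.9% | Φ(0) = 50.0% |
| 2 (planned) | Φ(0.75) = 77.3% | Φ(0.5) = 69.1% |

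Setting the whole-number rate to 55% gives m = 0.5 + 2 × 0.1257 = 0.75, which lies inside the primary null hypothesis. The continuous reading gives m = 1 + 2 × 0.1257 = 1.25, just outside it.

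**Chance of observing at least 55%** (binomial tail; whole-number score, with the continuous reading in brackets).

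| n | Responders needed | True decrease 0 | True decrease 1 | True decrease 2 |
|---|---|---|---|---|
| 36 | 20 | 0.044 (0.002) | 0.759 (0.309) | 0.999 (0.971) |
| 40 | 22 | 0.041 (0.001) | 0.786 (0.318) | 1.000 (0.980) |
| 45 | 25 | 0.026 (0.001) | 0.772 (0.276) | 1.000 (0.981) |
| 50 | 28 | 0.017 (0.000) | 0.760 (0.240) | 1.000 (0.983) |

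**Overlap with the primary test.** In simulated trials at a true decrease of 1 with whole-number scores, the t-test succeeds in about 5% of trials, and virtually all of those also reach 55%. Reaching 55% and failing the test therefore has probability of about 0.76 − 0.05 = 0.71 at n = 36 or 50, and up to 0.785 − 0.05 = 0.735 at n = 40.

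**Dependence on shape.** Mean and SD do not fix the rate. Suppose 45% of subjects are unchanged, 10% improve by 2 points, and 15% each improve by 3, 4 and 5 points. The mean decrease is 0.2 + 0.45 + 0.6 + 0.75 = 2.00. The variance is 0.4 + 0.15 × (9 + 16 + 25) − 4 = 3.9, so the SD is 1.97. The responder rate is exactly 55%. The stated floor is thus compatible with the planning values even as a point expectation.

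**The case for a change.** The best case for a change is that a numerical expectation in a protocol gets quoted in the report. On the reading that fits the instrument, a study at the null boundary meets this one about three times in four. Virtually every study that passes the primary test meets it too, so meeting it tells the reader almost nothing beyond the primary result. The interval is also wide at this size: 25 responders of 45 (55.6%) has an exact 95% interval of 40.0% to 70.4%, which takes in the 59.9% expected at the boundary. A short text could state the rates at the planned and null means, add the interval, and say that the responder rate cannot stand in for a failed primary endpoint.

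The arithmetic stands, and so does the missing basis for the 55%. The proposed text gains little, however:

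- The synopsis already makes the mean change the only route to success, so a disclaimer would repeat it.
- Replacing the 55% with a rate computed from a normal curve would exchange an unexplained figure for one resting on an unsupported shape. The score is bounded at 0 to 12, and entry requires at least 6.
- The null boundary is not an ineffective treatment. Section 13.2 sets the 1 unit at 2 to 4 times the evidence-based thresholds it cites (0.23 to 0.28, and 0.59). A majority of responders at a true mean decrease of 1 is what such a deliberately strict null would produce.

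**Conclusion.** No change is needed. The 55% is an undocumented and cautious floor on a descriptive measure. It agrees with the planning values, which imply about 77% on whole-number scores (69% on the continuous reading), and nothing in the plan is decided by it. An analyst who follows the plan as written reaches no wrong conclusion. The rate is a coarser summary of the primary variable, and the plan does not present it as independent confirmation.

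The floor is weak against the null boundary, where the chance of meeting it is 0.76 to 0.79 on whole-number scores and 0.24 to 0.32 on the continuous reading. It is informative against no mean change, where the chance is 0.02 to 0.04 on whole-number scores. These figures assume an approximately normal change with SD 2 and 36 to 50 subjects; another shape with nearly the same mean and SD can move the rate as far as 55%.

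An analyst can report the responder rate with an exact 95% interval without amending the plan. Documenting where the 55% came from would be tidy, but it would alter no result.

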13.4 Definition of Populations

Enrolled Population – all subjects enrolled in the study.

Evaluable Population – all subjects that are enrolled in the study and have received the study procedure. If a protocol revision is required after review of the initial subjects that substantially alters the treatment settings, a subgroup of the evaluable population will be defined to include only those subjects enrolled and treated under the revised protocol (revised protocol population). Results will be summarized for the evaluable population, the initial protocol population, and the revised protocol population (used for primary endpoint analysis).

Safety Population – all subjects that have received the study procedure

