13.5 Missing Data

All efforts will be made to collect all data points in this study. The study hypothesis will be tested using all available data for the subjects in the evaluable patient population. If the primary endpoint is not available for all such subjects, then sensitivity analysis will be performed to assess the potential effect of missing data on the study conclusion. The sensitivity analysis will be performed by imputing all missing data points for the primary endpoint as no (0) improvement. If the study conclusion is upheld using this type of worst-case scenario, no other analysis will be performed. However, if the conclusion using imputed data is different, a multiple imputation approach may be used to gain further insight to the results.

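### Does the expected 55% responder rate need a stated denominator, a missing-score rule and a source?

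*Combined protocol and SAP*

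**What the plan says.** The responder rate is listed in the Synopsis under the additional evaluations and in section 13.10 among the other efficacy measures. The Synopsis wording is: "A responder is defined as a treated subject who experiences at least a 1 point improvement (decrease) in the rTNSS score at 12 weeks". Section 13.10.1 says: "Subjects will be considered to have responded to treatment if they show a decrease of at least 1 point in the rTNSS score". Both then state: "An overall responder rate of at least 55% is expected for the study".

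Section 13.4 defines the evaluable population as everyone enrolled and treated; a 12-week score is not required. It says results will be summarized for that population. If the treatment settings are substantially revised after the first phase, it adds an initial-protocol group and "the revised protocol population (used for primary endpoint analysis".

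Section 13.5 tests the study hypothesis on all available data. If any primary-endpoint values are missing, it adds a sensitivity analysis "imputing all missing data points for the primary endpoint as no (0) improvement". It does not mention the responder rate.

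The sample-size assumptions in section 13.3 include "10% dropout and nonevaluable", a "2-point decrease in mean change score = the minimum expected observed difference" and "SD = 2 = the expected standard deviation of the observed mean difference". Study success is defined in the Synopsis by the mean change alone, which must be an improvement exceeding 1 point.

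**The concern.** A stated percentage invites a comparison once the results are in, and a percentage needs a denominator. The Synopsis says who can be a responder but not what the count is divided by. Section 13.5 is limited to the hypothesis and the primary endpoint. Two readings are therefore open: responders over treated subjects who have a 12-week score, or responders over all treated subjects with missing scores counted as failures. If the protocol is revised after phase 1, there is also a choice among three populations.

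The 55% itself has no stated origin. Sections 5.0 and 3.2.2 report 73% and 74% improving at 6 months, but the first is on SNOT-22, the second is for cryosurgery, and the plan links neither to 55%. Because rTNSS moves in whole points, a 1-point decrease is the smallest improvement that can be recorded, so the bar is low.

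At stake would be an uncontrolled study reporting that it reached its expected rate when the other denominator would say it had not, with the choice made after the data were seen. A reader might then take that statement as support for the primary claim.

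**Working it through.** **Inputs.** From section 13.3: 50 planned subjects, 10% loss, mean change -2, null value -1, SD 2, one-sided alpha 0.05, power 90%. From section 13.10.1: a 55% rate and a 1-point cut-off. My assumptions: all 50 subjects are treated and the 10% loss is entirely missing 12-week scores (45 scored); for the probabilities, change scores are normal and responders among the 45 scored are binomial.

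**The plan's own figure.** Paired t-test power with shift |-2 - (-1)| = 1 and SD 2 is 90.3% at n = 36 and 89.5% at n = 35, so the stated minimum of 36 is reproduced. The plan gives nothing from which 55% could be reproduced.

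**Where the two denominators disagree.**
- Scored only: 0.55 × 45 = 24.75, so 25 responders are needed.
- All treated: 0.55 × 50 = 27.5, so 28 are needed.

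| Responders | Of 45 scored | Of 50 treated |
|---|---|---|
| 24 | 53.3% | 48% |
| 25 | 55.6% | 50% |
| 26 | 57.8% | 52% |
| 27 | 60.0% | 54% |
| 28 | 62.2% | 56% |

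The readings split at 25, 26 and 27. The split narrows with fewer missing scores: at 3 or 4 missing, only 26 and 27 split; at 1 or 2, only 27 splits; at none, the readings coincide. If 10 phase-1 subjects were set aside (40 treated, 36 scored), the thresholds are 22 (0.55 × 40 = 22) and 20 (0.55 × 36 = 19.8), so 20 and 21 split.

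**How 55% compares with the sample-size assumptions.** For a whole-point score, the modelled chance that a scored subject responds is Φ((-0.5 - μ)/2). A continuous score would give Φ((-1 - μ)/2), which fits rTNSS less well.
- μ = -2: Φ(0.75) = 0.773 (continuous Φ(0.5) = 0.691).
- μ = -1: Φ(0.25) = 0.599 (continuous Φ(0) = 0.500).

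The expectation is a floor, and 69% to 77% lies above it, so there is no inconsistency with section 13.3. It is also near the 50% to 60% expected when the true mean sits at the null value, so reaching it says little about the primary hypothesis.

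**How often the choice would matter.** P(25 ≤ X ≤ 27) for X binomial with n = 45:
- μ = -2: 0.0065 whole-point (0.104 continuous).
- μ = -1: 0.336 whole-point (0.208 continuous).

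At zero mean change, the whole-point chance of reaching 55% of scored subjects, P(X ≥ 25), is 2.6% at SD 2, 4.7% at SD 2.5 and 6.8% at SD 3.

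**Size of the shift.** Counting 10% missing as non-response multiplies the rate by 0.9. At μ = -2 it falls from 0.773 to 0.696, or from 0.691 to 0.622: 7 to 8 points.

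**The case for a change.** The strongest case for a change is that the arithmetic needs no distributional model, the gap is real, and the remedy is a sentence or two. Naming treated subjects settles who may be called a responder, but a rate among treated subjects with a score still fits the text. Section 13.5 cannot be read as covering this measure without extending it. With no control group, 55% is the only yardstick the plan gives for this rate. If the true mean change is near 1 point, the two readings would disagree in roughly a fifth to a third of trials.

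Much of this stands: section 13.5 has no rule for this measure, 55% has no derivation, and the split at 25 to 27 is exact for 45 of 50. Three parts do not carry the weight put on them.

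- The denominator is not wholly unstated. The Synopsis refers to treated subjects and section 13.4 summarizes results for the treated population. Only the handling of unscored subjects is open.
- The choice among three populations arises only after a substantial change in settings, and the plan then reports results for all three.
- The 45-of-50 case takes the whole allowance as missing scores in treated subjects. Section 13.7 foresees subjects enrolled but not treated, who belong to neither denominator, so the number unscored among those treated could be smaller.

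Making missing-as-failure the main rule would also reverse the order in section 13.5, where available data come first and zero improvement is the sensitivity analysis. Further cut-offs and exact intervals are preferences.

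**Conclusion.** No change is needed. What remains is a missing detail in a descriptive measure: how a treated subject without a 12-week rTNSS enters the responder rate, and where 55% comes from. An analyst following section 13.5 by analogy would report the available-data rate, with missing counted as non-response as a check. With the counts shown, a reader can compute either version.

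With 5 of 50 unscored, the two versions lie on opposite sides of 55% for three possible counts; with 1 or 2 unscored, for one. At the planned effect they disagree in under 1% of trials on the whole-point model, or about 10% on the continuous one. Near a true mean of -1 the figure is 21% to 34%, but the primary test, not this rate, judges whether the mean improvement exceeds 1 point. These probabilities rest on an assumed normal shape, SD 2 and 45 scored of 50.

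The plan treats 55% as an expectation, not a criterion. Following it as written gives no wrong conclusion about study success, and added wording would leave the design and primary analysis unchanged. The one caution is for interpretation: a rate above 55% should not be presented as evidence that the mean improvement exceeds 1 point.
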